14.3 Secondary Endpoint Justification

1. Safety and tolerability: Adverse events and immune-related adverse events by the current version of Common Terminology Criteria for Adverse Events version 4 (CTCAE v4.03) will be tabulated in order to assess the safety profile and tolerability therapy in treated patients.
2. Progression-free survival (PFS): PFS will be defined as the duration of time from start of treatment to time of recurrence, progression, or death due to any cause, whichever occurs first. Patients will be censored at last follow up date. The Kaplan Meier estimate of median PFS will be reported, as well as the PFS rate at 24 weeks (+/- 1 week).
3. Overall survival (OS): Overall survival will be evaluated using the Kaplan Meier Method.
4. Duration of response (DOR): Duration of response will be determined for each patient with time origin at the first occurrence of confirmed response (CR, PR) until the first occurrence of progression or date of death if the patient dies due to any cause before progression. Duration of response will be evaluated using the Kaplan Meier Method.

5. Clinical benefit rate (CBR): Clinical benefit rate will be defined as the percentage of patients with complete response (CR) + partial response (PR) + stable disease (SD) by 24 weeks from the start of treatment will be reported and the 90% confidence interval will be estimated using exact binomial proportions.
6. Best confirmed ORR, PFS, CBR, and DOR according to immune-related RECIST (irRECIST) as presented by Bohnsack et al.(53) and as proposed in [Appendix 5](#). The methodology is the same as described for RECIST 1.1 except for new lesions do not automatically denote disease progression and the measurement of longest diameter of new measurable lesions are included in the sum of the measurement of the original target lesions. This method accounts for some of the delayed response patterns seen with immune checkpoint blockade. The efficacy endpoints based on irRECIST will be estimated using the same methods for these endpoints based on RECIST.

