1.0 PROTOCOL SUMMARY AND/OR SCHEMA

This is a phase II study testing durvalumab and tremelimumab in metastatic, non-transitional cell carcinoma of the urothelial tract. Patients with I) any component of small cell carcinoma (or neuroendocrine features) II) predominant squamous cell carcinoma or III) predominant adenocarcinoma of the urothelial tract will be enrolled. A Simon's minimax two-stage design will be carried out. We will enroll 13 patients in the first stage. If we see 1 or more responses in the first stage, we continue to the second stage where we enroll an additional 14 patients for a total sample size of 27 patients. Patients will be treated in 4-week cycles. Patients will receive 4 cycles of the combination of durvalumab and tremelimumab followed by up to 9 cycles of durvalumab maintenance or until lack of clinical benefit or unacceptable toxicity. Cross-sectional imaging will be performed every 8 weeks until the end of treatment. The best, confirmed overall response rate (ORR) by RECIST 1.1 will be determined as the primary endpoint.

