10.3 Radiographic Studies During Treatment

Patients will undergo cross-sectional imaging every 2 cycles (\pm 7 days) until lack of clinical benefit. CT chest may be with or without contrast. MRI chest may be performed if patients refuse CT. Abdomen/Pelvis imaging should include IV contrast unless there is an extenuating circumstance approved by the PI. CT scans of the abdomen/pelvis and MRI abdomen/pelvis are both acceptable. Imaging will be evaluated using RECIST v1.1.

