12.1 CRITERIA FOR THERAPEUTIC RESPONSE/OUTCOME ASSESSMENT

Patients will be assessed every cycle by physical examination for response for disease progression. Patients will have appropriate radiographic diagnostic procedures (CT scan of chest and CT or MRI of abdomen and pelvis) for evaluation of measurable disease at baseline within 28 days of initiation of the study. Imaging will be repeated to evaluate the disease every 2 cycles while patients are on study.

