Subjects who are permanently discontinued from further receipt of investigational product, regardless of the reason (withdrawal of consent, due to an AE, other), will be identified as having permanently discontinued treatment.

Subjects who are permanently discontinued from receiving investigational product will be followed per section 9.4 for safety, including the collection of any protocol-specified blood specimens, unless consent is withdrawn or the subject is lost to follow-up or enrolled in another clinical study. All subjects will be followed for survival. Subjects who decline to return to the site for evaluations will be offered follow-up by phone every 3 months as an alternative.

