^a “Non-CR/non-PD” is preferred over “stable disease” for non-target disease since stable disease is increasingly used as an endpoint for assessment of efficacy in some trials; thus, assigning “stable disease” when no lesions can be measured is not advised.

B. Missing Assessments and Not-Evaluable Designation

When no imaging/measurement is done at all at a particular timepoint, the patient is not evaluable at that timepoint. If only a subset of lesion measurements are made at an assessment, usually the case is also considered not evaluable at that timepoint, unless a convincing argument can be made that the contribution of the individual missing lesion(s) would not change the assigned timepoint response. This would be most likely to happen in the case of PD. For example, if a patient had a baseline sum of 50 mm with three measured lesions and, during the study, only two lesions were assessed, but those gave a sum of 80 mm; the patient will have achieved PD status, regardless of the contribution of the missing lesion.

If one or more target lesions were not assessed either because the scan was not done or the scan could not be assessed because of poor image quality or obstructed view, the response for target lesions should be “unable to assess” since the patient is not evaluable. Similarly, if one or more non-target lesions are not assessed, the response for non-target lesions should be “unable to assess” except where there is clear progression. Overall response would be “unable to assess” if either the target response or the non-target response is “unable to assess,” except where this is clear evidence of progression as this equates with the case being not evaluable at that timepoint.

Table 3. Best Overall Response When Confirmation Is Required

Overall Response at First Timepoint	Overall Response at Subsequent Timepoint	Best Overall Response
CR	CR	CR
CR	PR	SD, PD, or PR ^a
CR	SD	SD, provided minimum duration for SD was met; otherwise, PD
CR	PD	SD, provided minimum duration for SD was met; otherwise, PD
CR	NE	SD, provided minimum duration for SD was met; otherwise, NE
PR	CR	PR
PR	PR	PR
PR	SD	SD
PR	PD	SD, provided minimum duration for SD was met; otherwise, PD
PR	NE	SD, provided minimum duration for SD was met; otherwise, NE
NE	NE	NE

CR = complete response; NE = not evaluable; PD = progressive disease; PR = partial response;
 SD = stable disease.

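### PFS is censored at the last follow-up date, not the last tumour assessment, so any unscanned follow-up counts as progression-free time (minor)

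*Combined protocol and SAP*

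**What the plan says.** Section 14.3, item 2 measures PFS from start of treatment to recurrence, progression or death from any cause. It reports the Kaplan-Meier median and a 24-week rate. The whole censoring rule is "Patients will be censored at last follow up date". Item 4 gives DOR no censoring rule and says only "Duration of response will be evaluated using the Kaplan Meier Method". Item 6 carries the same methods over to the irRECIST versions.

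On imaging, section 12.1 says "Imaging will be repeated to evaluate the disease every 2 cycles while patients are on study". After treatment, section 10.4 refers to Appendix 2. That appendix continues scans until confirmed progression for patients who finish treatment with disease control, or who stop for toxicity or symptomatic deterioration.

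Follow-up is wider than imaging. Section 13.1 requires survival follow-up for everyone. It allows, but does not require, progression follow-up in patients who stop treatment while keeping consent, and it adds: "Subjects who decline to return to the site for evaluations will be offered follow-up by phone every 3 months". The footnotes to Appendices 2 and 3 let survival status and later therapy be collected by telephone.

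**The concern.** Progression is observed only when someone looks for it. A patient known by telephone to be alive at week 40, but last scanned at week 8, is known to be progression-free only to week 8. Under the stated rule that patient stays in the PFS risk set to week 40. The protocol's own RECIST appendix takes the same view of a missing scan: "When no imaging/measurement is done at all at a particular timepoint, the patient is not evaluable at that timepoint". That sentence governs response at a timepoint, not PFS censoring, but it shows that no scan means no information about progression.

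The direction is fixed. With the same events, later censoring enlarges the risk sets, so each Kaplan-Meier factor 1 - d/n stays equal or rises. What is at stake is a modest upward bias in PFS by RECIST 1.1 and by irRECIST. In a single-arm trial those figures are likely to be read beside outside results. DOR is exposed to the same choice because its rule is unstated.

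**Working it through.** **What the plan gives.** There is no PFS assumption, target or test, so there is no PFS figure to reproduce. The only design figure is the Simon minimax design for response in section 14.2: 13 then 27 patients, stop at 0 of 13, success at 4 or more of 27, rates 5% and 20%. Summing P(X1 = x) × P(X2 ≥ 4 - x) over x = 1 to 13, with X1 from 13 patients and X2 from 14, gives exact type I error 0.0416 and power 0.8011. The design reproduces, and PFS plays no part in it.

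**Inputs.** From the documents: 27 patients and scans every 8 weeks (sections 4.2 and 10.3). Assumed: progression in 7, 6 and 4 patients at weeks 8, 16 and 24; k others last scanned at week 8 but alive and in contact past week 24; no other censoring before then.

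**Stated rule.** The k patients stay at risk throughout:

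(20/27) × (14/20) × (10/14) = 10/27 = 37.0%, whatever k is.

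**Last-scan rule.** The k patients leave after week 8:

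(20/27) × (1 - 6/(20 - k)) × (1 - 4/(14 - k))

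| k | Calculation | Last-scan rule | Stated rule |
|---|---|---|---|
| 1 | (20/27)(13/19)(9/13) | 35.1% | 37.0% |
| 2 | (20/27)(12/18)(8/12) | 32.9% | 37.0% |
| 3 | (20/27)(11/17)(7/11) | 30.5% | 37.0% |

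**General form.** Suppose n patients are at risk just after the last scan of the k patients, and a share q of the n - k still scanned remain event-free at the landmark. The stated rule gives [k + (n - k)q]/27 and the last-scan rule gives nq/27. The difference is k(1 - q)/27. For k = 3, q = 7/17 and 3 × (10/17)/27 = 6.5 points, as in the table. The ceiling is 1/27 = 3.7 points per patient.

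**Range per patient.** Take assumed exponential PFS with medians of 16 to 8 weeks, so that q = 2^(-gap/median), where gap is the time from last scan to week 24:

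- last scan at week 16: 1.1 to 1.9 points
- last scan at week 8: 1.9 to 2.8 points
- no scan after baseline: 2.4 to 3.2 points

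**Range for the trial.** The number affected is not in the documents, so two sets of assumptions were simulated.

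1. An overall 5, 10, 20 or 30% of patients leave imaging; PFS medians are 8 to 16 weeks; later deaths count as events under both rules. The median shift at week 25 is 0.55, 0.9, 1.5 and 2.1 points, and the whole range is 0.03 to 6.7.
2. A harsher case: a 10% or 20% chance of leaving imaging at every scan after the first, everyone alive and in contact to week 52, PFS medians 12 to 26 weeks. The shift at week 24 is about 4 to 5 points (10%) or 8 to 11 points (20%).

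For scale, the standard error of 10/27 is the square root of (10/27)(17/27)/27, or 9.3 points.

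**The case against.** The best reply is that the plan leaves little unscanned follow-up. Appendix 2 scans patients who stop for toxicity or symptomatic deterioration as well as those who finish treatment with disease control. Withdrawal of consent ends observation (section 13.1), and withdrawal before the first scan leads to replacement (section 14.2). Patients with confirmed progression, whom sections 9.4 and 10.4 send to Appendix 3 with its optional scans, already have their event. If last follow-up were taken to mean the last scan, the effect would be zero. All of this stands as a limit on size. It does not remove the patients who decline visits, or those who stop treatment or change therapy and are followed only for survival. The text also does not say that follow-up means scanning.

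A reader might infer more than the documents support:

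- **That imaging simply stops at the end of treatment.** Section 1.0 says "Cross-sectional imaging will be performed every 8 weeks until the end of treatment", but it is a summary. Section 10.3 covers the treatment period, and footnote 9 of the section 10 schedule sends post-treatment imaging to section 10.4 and so to Appendix 2. Together these are an on-treatment rule and a post-treatment rule.
- **That section 9.4 opens another unscanned route.** It lets assessments at the end-of-treatment visit be skipped. It does not cancel later Appendix 2 scans.
- **That PFS leaves open whether clinical progression is an event.** Section 2.1 defines PFS by RECIST 1.1, and Appendix 4 treats symptomatic deterioration as a reason for stopping therapy, not an objective outcome.
- **That the 24-week rate is unreadable.** Its one-week tolerance matches the scan window. Assigning in-window scans to week 24 and reading the curve at week 25 agree to within 0.3 point in simulation. A bias of 5 to 8 points arises only if the tolerance is ignored and the curve is read at exactly week 24.0, with assumed medians and scan timing.

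**Conclusion.** The concern holds as a minor correction to the PFS censoring rule. The wording credits unscanned time as progression-free for patients alive without documented progression, and the bias can only be zero or upward. Patients who die are events under both rules, so only those still alive at analysis matter.

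The size rests on an unknown count. Each such patient adds at most 3.7 points to the week-24 estimate, and 1.1 to 3.2 under the assumed exponential medians of 8 to 16 weeks. With modest overall loss from imaging, the typical shift is below one patient in 27; only sustained loss at every scan, with everyone still in contact, brings it near the standard error. The simulated summaries describe assumed settings and are not probabilities.

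PFS is secondary, descriptive and untested. The sample size, the stage 1 rule and the threshold of 4 responses in 27 do not change, so it would be wrong to infer that the trial's conclusion on activity is at risk.

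**What to change.** Replace the censoring sentence in section 14.3, item 2 with: *Patients alive without documented progression by the applicable criteria are censored at the date of the last evaluable tumour assessment (start of treatment if there is none after baseline); death from any cause remains an event.*

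Apply the same rule to irRECIST PFS, and to DOR by both criteria. DOR needs no special clause for patients without a later scan: section 12.3 requires confirmation of response, so an assessment at or after the DOR origin always exists.

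The cost is a sentence or two in section 14.3 and no new data, since tumour assessments are already recorded. Reported PFS may be slightly lower. The change stops crediting unobserved time but does not recover progression that was never scanned. In the first simulation, with 10 to 30% leaving imaging, last-scan censoring still sat 1.0 to 14.4 points above complete scanning, the upper end arising when patients left just before the scan that would have shown progression. Keeping patients on the Appendix 2 scans therefore still matters.

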14.4 Exploratory analyses

Listed below are immune related hypotheses and the plan for exploratory analyses. Additional or different investigational methods will be used to characterize and measure components of the immune response based upon the latest available technology at the time of analysis. Specimens will also be stored for future studies related to non-TCC of the urothelial tract immunity for those patients who have consented to an institutional biobanking protocol (e.g. 06-107, 12-245, etc). If tissue availability or funding is limited, assay priority will be determined at the investigators discretion.

The exploratory hypotheses listed below are hypothesis generating. As such, all four of the exploratory analyses will be descriptive and graphical in nature. To test the associations between binary CBR or subtypes and biomarkers we will use Fisher's exact or Wilcoxon rank sum tests for binary or continuous variables respectively.

Immune Hypothesis 1: The tumor microenvironment will vary based on the histologic subtype of non-TCC of urothelial tract.

Proposed biomarker evaluation: Analysis of immune infiltrate will be performed using immunohistochemistry (IHC), immunofluorescence (IF), and computational approaches based upon RNA sequencing data. Immune regulatory molecules and populations of cells analyzed may include, but will not be limited to PD-L1, CD4, CD8, Tregs, B cells, macrophages, and dendritic cells and expression of biologically relevant/phenotypic markers thereof. The Ventana SP263 assay (performed in accordance with the package insert on the Ventana Benchmark platform (Ultra or XT) should be used to measure PD-L1.

Immune Hypothesis 2: The composition and phenotype of the tumor microenvironment at baseline will correlate with the clinical benefit rate (CBR).

Proposed Biomarker Evaluation: See immune hypothesis 1.

Immune Hypothesis 3: High T cell clonality in the tumor plus peripheral expansion of dominant tumor-resident T cell receptor clones will be associated with the CBR.

Proposed Biomarker Evaluation: We will perform high throughput DNA sequencing of the CDR3 region of the TCR beta chain in baseline tumors and pre- and post-treatment peripheral blood.

Immune Hypothesis 4: High levels of myeloid derived suppressor cells (MDSCs) and T regulatory cells (Tregs) in the peripheral blood and high levels of immunosuppressive tumor associated myeloid cells and T regulatory cells in will correlate with a decreased CBR.

Proposed Biomarker Evaluation: We will perform a whole blood flow cytometry based assay to determine the MDSC and Treg percentage in pre- and post-treatment blood samples. We will analyze tumor associated myeloid cells and T regulatory cells in the tumor using immunohistochemistry (IHC), immunofluorescence (IF), and computational approaches based upon RNA sequencing data.

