2.1 OBJECTIVES AND SCIENTIFIC AIMS

Primary Objective:

- To determine the efficacy of the combination of durvalumab and tremelimumab in patients with I) carcinoma with a small-cell component (or neuroendocrine features) II) predominant squamous cell carcinoma or III) predominant adenocarcinoma or the urothelial tract as measured by best ORR, which will include the sum of complete response (CR) + partial response (PR) by RECIST v 1.1.

Secondary Objectives:

- To assess for other parameters of clinical outcome of the combination of durvalumab plus tremelimumab in patients with I) carcinoma with a small-cell component (or neuroendocrine features) II) predominant squamous cell carcinoma or III) predominant adenocarcinoma or the urothelial tract including:
 - Progression Free Survival (PFS) and duration of response (DOR) rate by RECIST v1.1
 - Overall survival (OS)
 - Best ORR (CR + PR), PFS, and DOR by Immune-related Response Criteria in Solid Tumors (irRECIST) criteria
 - Clinical benefit (CR + PR + Stable Disease [SD]) rate by RECIST v1.1 and irRECIST
 - Rate of immune-related Adverse Events (irAE)
 - Rate of serious adverse events (SAE)

Exploratory Objectives:

- To determine differences in the immune microenvironment between bladder cancer histologies as determined by PD-L1 staining, immune related gene expression profiles, and multiplex immunofluorescence (IF) for multiple immune cell subsets
- To determine whether bladder cancer histology and the associated immune microenvironment as defined above is predictive of the clinical benefit rate (CBR).
- To determine if T cell clonality in tumors and blood will be associated with the CBR.
- To determine whether immune suppressive cells types in the peripheral blood and in tumors will correlate with a decreased CBR.

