4.1 OVERVIEW OF STUDY DESIGN/INTERVENTION

4.2 Design

This is a single-arm, phase II study with a Simon minimax design testing the combination of durvalumab and tremelimumab in patients with non-TCC of the urothelial tract. In the first stage, 13 patients will be accrued. If there are no responses in these 13 patients, the study will be stopped. Otherwise, 14 additional patients will be accrued for a total of 27. The null hypothesis will be rejected if 4 or more responses are observed in 27 patients. See section 14 for more details regarding statistical design.

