14.1 BIOSTATISTICS

14.2 Primary Endpoint and Sample Size Justification

The three histologic groups (Small-Cell, Squamous Cell Carcinoma, and Adenocarcinoma) will be part of the same cohort given they are expected to have similar response rates. With an unacceptable rate of 5% and acceptable rate of 20%, and setting type I error to 5% and power to 80%, with Simon's minimax two-stage design, we will enroll 13 patients in the first stage. Non-transitional cell carcinoma of the urothelial tract is a rare entity. Single, arm phase II studies have been published, but only in the front-line setting and only in small cohorts of patients (summarized in table 1). To our knowledge, there is no published data on response rates to second-line chemotherapy in patients with non-transitional cell carcinoma of the urothelial tract. The patient population under study has no standard treatment options and, in our group's clinical experience, rarely experiences a meaningful clinical benefit from chemotherapy. Therefore, we have elected to set the null hypothesis at an ORR of 5%. If no

patients in the first 13 have achieved a response, enrollment for stage 2 will be halted until the 13 subjects in the first stage have been assessed for response (window of 2 disease assessment scans following initiation of treatment). If we see 1 or more responses in any of the histologies in the first stage, we continue to the second stage where we will enroll additional 14 patients. If, at the end of the study, we see 4 or more responses out of the total of 27 patients, we will consider the therapy promising. As an exploratory analysis, we will also estimate the response rate of the small cell/neuroendocrine, predominant squamous, and predominant adenocarcinoma cohorts separately as a proportion of responders with the corresponding confidence interval, although formal comparisons between the three cohorts are not planned.

The response evaluable population is defined as all patients with a baseline disease assessment who have received at least one treatment with durvalumab and tremelimumab on study and have had either at least one post-baseline disease assessment or withdrawn from study treatment prior to post-baseline disease assessment due to clinical progression or death.

As described in section 9.2, patients may undergo retreatment after disease progression. The primary endpoint of best overall response is based on the best response from the first round of treatment.

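### The marker–CBR tests in section 14.4 pool three histologies, so an association with a tumor marker cannot be separated from histology; a stratified sensitivity analysis is missing

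*Combined protocol and SAP*

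**What the plan says.** Section 14.4 gives one sentence of method for the marker analyses. It opens with "To test the associations between binary CBR or subtypes and biomarkers we will use" and then names two tests: Fisher's for binary markers and the rank-sum test for continuous ones. Nothing there or elsewhere stratifies or adjusts these tests by histology.

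Three other statements bear on this:

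- Immune Hypothesis 1 in section 14.4: "The tumor microenvironment will vary based on the histologic subtype of non-TCC of urothelial tract". Immune Hypothesis 2 then relates baseline microenvironment to CBR and refers back to Hypothesis 1 for its marker panel, so the same markers appear in both.
- The second exploratory objective in section 2.1: "To determine whether bladder cancer histology and the associated immune microenvironment as defined above is predictive of the clinical benefit rate (CBR".
- Section 14.2 says the three histologic groups "will be part of the same cohort given they are expected to have similar response rates".

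Section 14.4 also labels the four analyses hypothesis-generating and describes them as descriptive and graphical. Histology is known for every patient at entry (section 6.2, inclusion criterion 3).

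**The concern.** Histology confounds a marker–CBR comparison if it is related to both the marker and CBR. The protocol hypothesises the first link for tumor markers and raises the second as an open question. Eligibility adds a possible route for the second link: small cell patients must have progressed after prior systemic therapy, while squamous and adenocarcinoma patients may be untreated (section 6.2, criterion 8).

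At stake is how a positive marker finding is read. A pooled p-value would look the same whether the marker relates to benefit among patients of one histology or merely identifies the histology that does better. The second reading says nothing new about the microenvironment, and a reader of the pooled result alone could not tell the two apart.

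**Working it through.** **The plan's own figure.** Section 14.4 states none. The design behind the 27 patients is the Simon rule: 13 then 14 patients, stop at 0 responses in stage 1, and "The null hypothesis will be rejected if 4 or more responses are observed in 27 patients". With response rates of 5% and 20%, exact two-stage binomial calculation gives type I error 0.0416 and power 0.801, within the stated 5% and 80%. The design reproduces and is not in question.

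**Why pooling matters.** Let histology h have n_h patients, marker mean μ_h and CBR p_h, with marker and benefit independent within h. The expected pooled marker means are:

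- with benefit: Σ n_h p_h μ_h / Σ n_h p_h
- without benefit: Σ n_h (1 − p_h) μ_h / Σ n_h (1 − p_h)

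With 9 patients per histology, n_h cancels:

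- Large differences (μ = 0/1/2 SD, p = 20/40/60%): (0 + 0.4 + 1.2)/1.2 = 1.33 against (0 + 0.6 + 0.8)/1.8 = 0.78, a spurious gap of about 0.56 SD.
- Mild differences (μ = 0/0.5/1 SD, p = 20/35/50%): (0 + 0.175 + 0.5)/1.05 = 0.64 against (0 + 0.325 + 0.5)/1.95 = 0.42, a gap of 0.22 SD.
- Equal p_h or equal μ_h: gap 0.

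Both differences are therefore needed.

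**Inputs to the simulation.** N = 27 is from the protocol. The marker means, CBRs, histology mix and two-sided 5% level are assumptions. The 18/6/3 mix uses midpoints of the bladder-tumor ranges in section 3.2 (squamous 4%, adenocarcinoma 1.25%, small cell 0.75%; total 6%): 27 × 4/6 = 18, 27 × 1.25/6 ≈ 6, 27 × 0.75/6 ≈ 3. It is only one possible mix. The trial counts any small cell element as small cell and admits sites beyond the bladder.

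**Tests compared.** The pooled Wilcoxon rank-sum test, and the van Elteren test: ranks within histology, weight w_h = 1/(n_h + 1), z = (T − E)/√V. Here k_h is the number with benefit, T = Σ w_h × (rank sum of those with benefit), E = Σ w_h k_h (n_h + 1)/2, and V = Σ w_h² k_h (n_h − k_h) Σ(R − R̄)² / [n_h (n_h − 1)].

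**False-positive rate, continuous marker (6,000 simulated trials per row):**

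| Assumed differences | Mix | Pooled | Stratified |
|---|---|---|---|
| Large | 9/9/9 | 0.189 | 0.049 |
| Large | 18/6/3 | 0.129 | 0.048 |
| Mild | 9/9/9 | 0.077 | 0.049 |
| Mild | 18/6/3 | 0.064 | 0.045 |
| CBR equal | 9/9/9 | 0.047 | 0.053 |
| CBR equal | 18/6/3 | 0.050 | 0.055 |

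Repeat runs moved the pooled rates by about one percentage point, hence the rounded ranges of 6–9% and 13–20%.

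**Binary marker (10,000 trials, 9/9/9, marker prevalence 20/50/80%).** Pooled Fisher rejects in 0.03 of trials with CBR 35% throughout, 0.05 with CBR 25/35/45%, and 0.10 with CBR 15/35/55%. The exact stratified test stays at about 0.02. Fisher's test is conservative at this size, so its inflation shows later.

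**Power if histology acts through the marker.** Benefit depends only on the marker (logistic, slope 1 per SD, intercept −0.5 at the overall marker centre), with marker means 0/1/2 SD. Power is about 75% pooled against 46% stratified (9/9/9), and 66% against 41% (18/6/3).

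**The case against.** The strongest reply has four parts.

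1. *The analyses are labelled hypothesis-generating.* No decision rule rests on a marker p-value, and the 5% level is the reviewer's assumption. This stands and limits the importance of the point. It does not remove it, because formal tests are named and their results will be read.

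2. *Section 14.2 expects the histologies to respond alike, and inflation vanishes if CBR is equal.* The second half is correct. The first concerns response rate. CBR also counts stable disease (section 14.3), and section 2.1 treats its relation to histology as open. Still, nothing in the documents supports a threefold CBR gradient, so the 13–20% figures illustrate what could happen and are not a forecast.

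3. *Histology may act through the microenvironment.* The wording of the second exploratory objective fits that reading. The pooled association is then real, and stratifying discards part of it, as the power figures show. This stands and decides the form of the fix. The cost can also run the other way: with equal CBR, marker means 0/1/2 SD and a true 1-SD effect within histology, power was 38% pooled against 52% stratified (9/9/9). Neither test is better in every case.

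4. *Not every marker is affected.* A reader might infer that histology confounds all the marker–CBR tests. The documents do not support that. Hypothesis 1 concerns the tumor microenvironment; peripheral T-cell expansion and blood myeloid suppressor and regulatory T-cell levels are not said to differ by histology.

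**Conclusion.** The point holds as a gap in the exploratory plan. For tumor markers (Hypothesis 2 and the tumor parts of Hypotheses 3 and 4), the pooled tests cannot separate a marker signal from a histology label. The false-positive rate for a continuous marker is about 6–9% under mild and 13–20% under large assumed differences, and about 5% if CBR does not vary by histology. The marker differences, CBRs and histology mix behind these figures are all assumptions.

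Two stronger inferences are not supported. One is that the pooled tests are invalid and should give way to stratified ones: that depends on whether histology is a confounder or acts through the marker, which the documents leave open. The other is that the trial's main conclusion is at risk: the response endpoint, the two-stage rule and the sample size do not use these tests.

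**What to change.** Keep the planned pooled tests in section 14.4 and add three things:

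- a sensitivity analysis stratified by the three histologic groups, reported beside the pooled result: van Elteren for continuous markers, exact Cochran–Mantel–Haenszel for binary markers;
- plots of each marker by CBR status within histology;
- a sentence stating that a pooled association not seen within histology may reflect histology.

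The cost is a few sentences and a little more analysis, with no new data. The stratified test will have low power with 27 patients in three strata, and a histology in which all or none benefit contributes nothing. A non-significant stratified result should therefore not be read as evidence against a marker.
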